13.10.16. Rhabdomyolysis

Medical concept of rhabdomyolysis. Only narrow terms only for SMQ
 'Rhabdomyolysis/myopathy' plus 2 additional preferred terms selected from HGLT
 'muscle disorders' under SOC 'Musculoskeletal and connective tissue disorders'.

SMQ: 'Rhabdomyolysis/myopathy' SMQ Code: 20000002 Category: A Scope: Narrow	
Preferred Term	PT Code
Muscle necrosis	10028320
Myoglobin blood increased	10028625
Myoglobin blood present	10059888
Myoglobin urine present	10028631
Myoglobinaemia	10058735
Myoglobinuria	10028629
Myopathy	10028641
Myopathy toxic	10028648
Necrotising myositis	10074769
Rhabdomyolysis	10039020
Thyrotoxic myopathy	10081524
PTs (Select) from HGLT muscle disorders, HLGT Code 10028302	
Preferred Term	PT Code
Myalgia	10028411
Myositis	10028653

13.10.17. Pancreatitis

Medical concept of acute pancreatitis. Only narrow terms of SMQ 'Acute pancreatitis' selected. Algorithmic approach for this SMQ not used due to complexity in applying and poor specificity of remaining categories. Category A selected as PTs because more specific for concept (only narrow terms).

SMQ: 'Acute pancreatitis' SMQ Code: 20000022 Category: A Scope: Narrow	
Preferred Term	PT Code
Cullen's sign	10059029
Grey Turner's sign	10075426
Haemorrhagic necrotic pancreatitis	10076058
Hereditary pancreatitis	10056976
Immune-mediated pancreatitis	10083072
Ischaemic pancreatitis	10066127
Oedematous pancreatitis	10052400
Pancreatic abscess	10048984
Pancreatic cyst drainage	10082531
Pancreatic haemorrhage	10033625
Pancreatic necrosis	10058096
Pancreatic phlegmon	10056975
Pancreatic pseudoaneurysm	10081762
Pancreatic pseudocyst	10033635
Pancreatic pseudocyst drainage	10033636
Pancreatic pseudocyst haemorrhage	10083813
Pancreatic pseudocyst rupture	10083811
Pancreatitis	10033645
Pancreatitis acute	10033647
Pancreatitis haemorrhagic	10033650
Pancreatitis necrotising	10033654

SMQ: 'Acute pancreatitis' SMQ Code: 20000022 Category: A Scope: Narrow	
Preferred Term	PT Code
Pancreatitis relapsing	10033657
Pancreatorenal syndrome	10056277

13.10.18. Impact on Creatinine

Medical concept of worsening renal function/renal failure in the context of impact on creatinine. Only narrow terms from SMQ 'Acute renal failure' plus all PTs from HLT 'Renal failure and impairment', under SOC 'Renal and urinary disorders'. Numerous duplicated preferred terms e.g. renal failure

SMQ: 'Acute renal failure' SMQ Code: 20000003 Category: A Scope: Narrow	
Preferred Term	PT Code
Acute kidney injury	10069339
Acute phosphate nephropathy	10069688
Anuria	10002847
Azotaemia	10003885
Continuous haemodiafiltration	10066338
Dialysis	10061105
Foetal renal impairment	10078987
Haemodialysis	10018875
Haemofiltration	10053090
Neonatal anuria	10049778
Nephropathy toxic	10029155
Oliguria	10030302
Peritoneal dialysis	10034660
Prerenal failure	10072370
Renal failure	10038435

SMQ: 'Acute renal failure' SMQ Code: 20000003 Category: A Scope: Narrow	
Preferred Term	PT Code
Renal failure neonatal	10038447
Renal impairment	10062237
Renal impairment neonatal	10049776
Subacute kidney injury	10081980
Renal Failure and Impairment HLT, HLT Code 10038443	
Preferred Term	PT Code
Acute Kidney injury	10069339
Anuria	10002847
Atypical haemolytic uraemic syndrome	10079840
Cardiorenal syndrome	10068230
Chronic kidney disease	10064848
Crush syndrome	10050702
Diabetic end stage renal disease	10012660
End stage renal disease	10077512
Foetal renal impairment	10078987
Haemolytic uraemic syndrome	10018932
Hepatorenal failure	10019845
Hepatorenal syndrome	10019846
Nail-patella syndrome	10063431
Neonatal anuria	10049778
Oliguria	10030302
Pancreatorenal syndrome	10056277
Postoperative renal failure	10056675
Postrenal failure	10059345
Prerenal failure	10072370

SMQ: 'Acute renal failure' SMQ Code: 20000003 Category: A Scope: Narrow	
Preferred Term	PT Code
Propofol infusion syndrome	10063181
Renal failure	10038435
Renal failure neonatal	10038447
Renal impairment	10062237
Renal impairment neonatal	10049776
Renal injury	10061481
Scleroderma renal crisis	10062553
Traumatic anuria	10044501

13.10.19. Safety During Pregnancy

Use AE terms co-reported in pregnancy exposures to CAB.

13.11. Appendix 11: Identification of COVID-19 Adverse Events

COVID-19 adverse events are identified based on MedDRA coded values and/or AE referenced in the COVID-19 Coronavirus Infection assessment. The Lowest Level Terms (LLTs) and codes, Preferred Terms (PTs), High Level Terms (HLTs), High Level Group Terms (HLGTs), and System Organ Classes (SOCs), below are from MedDRA 23.0. In case there is a change to the version of MedDRA at time of reporting, the coded values based on the MedDRA version at the time of reporting will be used. The additional events may also be added based on the blinded review of AE data collected on study prior to the database freeze.

SOC: Infections and infestations

LLT code	LLT	PT	HLT	HLGT
10084459	Asymptomatic COVID-19	Asymptomatic COVID-19	Coronavirus infections	Viral infectious disorders
10084467	Asymptomatic SARS-CoV-2 infection	Asymptomatic COVID-19	Coronavirus infections	Viral infectious disorders
10053983	Corona virus infection	Coronavirus infection	Coronavirus infections	Viral infectious disorders
10051905	Coronavirus infection	Coronavirus infection	Coronavirus infections	Viral infectious disorders
10084382	Coronavirus disease 2019	COVID-19	Coronavirus infections	Viral infectious disorders
10084268	COVID-19	COVID-19	Coronavirus infections	Viral infectious disorders
10084401	COVID-19 respiratory infection	COVID-19	Coronavirus infections	Viral infectious disorders
10084270	SARS-CoV-2 acute respiratory disease	COVID-19	Coronavirus infections	Viral infectious disorders
10084272	SARS-CoV-2 infection	COVID-19	Coronavirus infections	Viral infectious disorders
10084381	Coronavirus pneumonia	COVID-19 pneumonia	Coronavirus infections	Viral infectious disorders
10084380	COVID-19 pneumonia	COVID-19 pneumonia	Coronavirus infections	Viral infectious disorders

LLT code	LLT	PT	HLT	HLGT
10084383	Novel COVID-19-infected pneumonia	COVID-19 pneumonia	Coronavirus infections	Viral infectious disorders
10084451	Suspected COVID-19	Suspected COVID-19	Coronavirus infections	Viral infectious disorders
10084452	Suspected SARS-CoV-2 infection	Suspected COVID-19	Coronavirus infections	Viral infectious disorders
10084461	SARS-CoV-2 carrier	SARS-CoV-2 carrier	Infectious disorders carrier	Ancillary infectious topics

13.12. Appendix 12: Abbreviations & Trade Marks

13.12.1. Abbreviations

Abbreviation	Description
ADaM	Analysis Data Model
AE	Adverse Event
AIC	Akaike's Information Criteria
A&R	Analysis and Reporting
CDISC	Clinical Data Interchange Standards Consortium
CI	Confidence Interval
CPMS	Clinical Pharmacology Modelling & Simulation
CS	Clinical Statistics
CSR	Clinical Study Report
CTR	Clinical Trial Register
CV _b / CV _w	Coefficient of Variation (Between) / Coefficient of Variation (Within)
DBF	Database Freeze
DBR	Database Release
DOB	Date of Birth
DP	Decimal Places
eCRF	Electronic Case Record Form
EEP	Efficacy Evaluatable Population
EMA	European Medicines Agency
FDA	Food and Drug Administration
FDAAA	Food and Drug Administration Clinical Results Disclosure Requirements
GSK	GlaxoSmithKline
IA	Interim Analysis
ICH	International Conference on Harmonization
IDMC	Independent Data Monitoring Committee
IDSL	Integrated Data Standards Library
IMMS	International Modules Management System
IP	Investigational Product
ITT	Intent-To-Treat
MMRM	Mixed Model Repeated Measures
PBMC	Peripheral Blood Mononuclear Cells
PCI	Potential Clinical Importance
PD	Pharmacodynamic
PDMP	Protocol Deviation Management Plan
PK	Pharmacokinetic
PP	Per Protocol
PopPK	Population PK
QC	Quality Control
QTcF	Frederica's QT Interval Corrected for Heart Rate
QTcB	Bazett's QT Interval Corrected for Heart Rate
RAP	Reporting & Analysis Plan
RAMOS	Randomization & Medication Ordering System
SAC	Statistical Analysis Complete

Abbreviation	Description
SDSP	Study Data Standardization Plan
SDTM	Study Data Tabulation Model
SOP	Standard Operation Procedure
TA	Therapeutic Area
TFL	Tables, Figures & Listings

13.12.2. Trademarks

Trademarks of the GlaxoSmithKline Group of Companies	Trademarks not owned by the GlaxoSmithKline Group of Companies
NONE	SAS

13.13. Appendix 13: List of Data Displays

All data displays will use the term “subject” rather than “participant” in accordance with CDSIC and GSK Statistical Display Standards.

Where applicable, all summary displays will present data across both the Intervention and Extension phases unless explicitly stated otherwise in the display title.

13.13.1. Data Display Numbering

The following numbering will be applied for RAP generated displays:

Section	Tables	Figures
Study Population	1.1 to 1.n	1.1 to 1.n
Efficacy	2.1 to 2.n	2.1 to 2.n
Safety	3.1 to 3.n	3.1 to 3.n
Pharmacokinetic	4.1 to 4.n	4.1 to 4.n
Virology	5.1 to 5.n	5.1 to 4.n
Other	6.1 to 6.n	6.1 to 6.n
Section	Listings	
ICH Listings	1 to x	
Other Listings	y to z	

13.13.2. Mock Example Shell Referencing

Nonstandard specifications will be referenced as indicated below (where a study specific mock shell is available) or the location of a similar display produced for a different study in the HARP reporting environment will be provided as reference. The example mock-up displays from other reporting efforts will be named in the format: Study Number/HARP Reporting Effort/Output Type (T/ F/L)/Display Number, where T stands for Table, F stands for Figure and L stands for Listing. For example, the Table 1.1 from primary_02 reporting effort for Study 201585 will be named by 201585/primary_02/T1.1. If required example mock-up displays provided in Appendix 14: Example Mock Shells for Data Displays.

Section	Figure	Table	Listing
Study Population	POP_Fn	POP_Tn	POP_Ln
Efficacy	EFF_Fn	EFF_Tn	EFF_Ln
Safety	SAF_Fn	SAF_Tn	SAF_Ln
Pharmacokinetic	PK_Fn	PK_Tn	PK_Ln
Virology	VIR_Fn	VIR_Tn	VIR_Ln
Other	OTR_Tn	OTR_Fn	OTR_Ln

13.13.3. Deliverables

Delivery	Description
HL	Month 12 Headline
M12	Month 12 Analysis
EOS	End of Study Analysis Note that the TLFs with asterisk (i.e. EOS*) will only be produced when the underlying source data has been changed since Month 12 analysis.

13.13.4. Study Population Tables

Study Population Tables					
No.	Population	GSK Standard / Example Shell	Title	Programming Notes	Deliverable
Subject Disposition					
1.1.	Safety	ES1	Summary of Subject Disposition for the Subject Conclusion Record	ICH E3, FDAAA, EudraCT	HL, M12, EOS
1.2.	Safety	SD1	Summary of Treatment Status and Reasons for Discontinuation of Study Treatment	ICH E3	M12, EOS
1.3.	Safety	ES4	Summary of Subject Disposition at Each Study Phase	ICH E3 Intervention/Extension phase: status and reason for withdrawal based on date and reason collected in the study treatment discontinuation form. Long term Follow-up: completion/withdrawal based on data collected in the Study Conclusion form.	M12, EOS
1.4.	Safety	ES5	Summary of Reason for Withdrawal at Each Study Phase	FDAAA, EudraCT	HL, M12, EOS
1.5.	Safety	ES11	Summary of Outcome of Adverse Events Which Led to Study Withdrawal/Treatment Discontinuation at Each Study Phase	EudraCT	M12, EOS
1.6.	Screened	ES6	Summary of Screening Status and Reasons for Screen Failure	Journal Requirements	M12, EOS

Study Population Tables					
No.	Population	GSK Standard / Example Shell	Title	Programming Notes	Deliverable
1.7.	Enrolled	NS1	Summary of Number of Subjects by Country and Site ID	EudraCT/Clinical Operations	M12, EOS
1.8.	Screened	NS1	Summary of Number of Subjects by Site Type and Site ID	Replace Country with Site Type Add column for Investigator Name	M12, EOS
Protocol Deviation					
1.9.	Enrolled	DV1	Summary of Important Protocol Deviations	ICH E3	M12, EOS
1.10.	Enrolled	DV1	Summary of Important COVID-19 Related Protocol Deviations	Update the label for the first row to be "ANY IMPORTANT COVID-19 RELATED PROTOCOL DEVIATIONS"	M12, EOS
1.11.	Enrolled	DV1	Summary of Important Non-COVID-19 Protocol Deviations	Update the label for the first row to be "ANY IMPORTANT NON-COVID-19 RELATED PROTOCOL DEVIATIONS"	M12, EOS
1.12.	Enrolled	DV1	Summary of All COVID-19 Protocol Deviations by Site	Update the label for the first row to be "ANY COVID-19 RELATED PROTOCOL DEVIATIONS". Summary for each site and 'Total' across sites.	HL, M12, EOS

Study Population Tables					
No.	Population	GSK Standard / Example Shell	Title	Programming Notes	Deliverable
1.13.	Enrolled	DV1	Summary of All Implementation Protocol Deviations by Site	Update the label for the first row to be "ANY IMPLEMENTATION RELATED PROTOCOL DEVIATIONS" Summary for each site and 'Total' across sites.	HL, M12, EOS
Population Analysed					
1.14.	Screened	SP1	Summary of Study Populations	GSK Statistical Display Standard	M12, EOS
1.15.	Enrolled	SP2	Summary of Exclusions from the Safety Population	GSK Statistical Display Standard	M12, EOS
Demographic and Baseline Characteristics					
1.16.	Safety	DM1	Summary of Demographic Characteristics	ICH E3, FDAAA, EudraCT. For EOS: add age group (18 - 24, 25 - 40, >40), BMI group (<30, >=30).	HL, M12, EOS
1.17.	Enrolled	DM11	Summary of Age Ranges	EudraCT	M12, EOS
1.18.	Safety	DM6	Summary of Race and Racial Combinations	ICH E3, FDA, FDAAA, EudraCT	M12, EOS
1.19.	Safety	BASELINE2	Distribution of CD4+ Cell Count Results at Screening and Baseline		M12, EOS*
1.20.	Safety	BASELINE3	Summary of Hepatitis Status at Entry		M12, EOS*
1.21.	Safety	CDC1	Summary of CDC Classification of HIV-1 Infection at Baseline		M12, EOS*

Study Population Tables					
No.	Population	GSK Standard / Example Shell	Title	Programming Notes	Deliverable
Prior and Concomitant Medications					
1.22.	Safety	MH1	Summary of Past Medical Conditions	ICH E3	M12, EOS*
1.23.	Safety	MH4	Summary of Past Cardiac, Gastrointestinal, Metabolism and Nutrition, Psychiatric, Renal and Urinary, Nervous System Conditions, and Hepatobiliary Disorders	ICH E3	M12, EOS*
1.24.	Safety	MH1	Summary of Current Medical Conditions	ICH E3	M12, EOS
1.25.	Safety	MH4	Summary of Current Cardiac, Gastrointestinal, Metabolism and Nutrition, Psychiatric, Renal and Urinary, Nervous System Conditions, and Hepatobiliary Disorders	ICH E3	M12, EOS
1.26.	Safety	CM9	Summary of Concomitant Medications by Ingredient Combinations	ICH E3 See GSK Statistical Display Standard Multi-ingredient medications will be labelled according to the sum of their ingredients, i.e., Generic Term.	M12, EOS
1.27.	Safety	207966/primary _15/T1.30	Summary of Prior Antiretroviral Therapy Medications	Remove the footnote. Follow definitions in Section 13.4.1 to determine the prior ART medications.	M12, EOS*

Study Population Tables					
No.	Population	GSK Standard / Example Shell	Title	Programming Notes	Deliverable
1.28.	Safety	201585/primary _02/T1.30	Summary of Antiretroviral Therapy Taken During Screening by Baseline Third Agent Class	Like Example shell but stratified by Baseline Third Agent Class (NNRTI,INI,PI); add 'Any' row under each class.	M12, EOS*
1.29.	Safety	RF1	Summary of HIV Risk Factors		M12, EOS*
Other					
1.30.	Safety	POP_T1	Summary of Transition to CAB + RPV LA Marketed Product Status by Site Type and Site ID		EOS

13.13.5. Efficacy Tables

Efficacy: Tables					
No.	Population	GSK Standard/Example Shell	Title	Programming Notes	Deliverable
Snapshot					
2.1.	Safety	EFF_T1 See Section 13.14	Summary of Study Outcomes (50 c/mL cutoff) at Month 12 (Intervention Phase) – Modified Snapshot Analysis with COVID-19 related LOCF	Missing HIV-1 RNA due to COVID-19 are imputing using last post baseline value carried forward.	HL, M12
2.2.	Safety	EFF_T2 See Section 13.14	Summary of Study Outcomes (50 c/mL cutoff) at Month 12 (Intervention Phase) –Snapshot Analysis	With expanded COVID-19 related/Non-related categories	HL, M12
2.3.	Safety	SNAPSHOT4	Proportion of Subjects with Plasma HIV-1 RNA \geq 50 c/mL Over Time (Intervention Phase) – Modified Snapshot Analysis with COVID-19 related LOCF	Missing HIV-1 RNA due to COVID-19 are imputing using last post baseline value carried forward. Use Exact (Clopper-Pearson) method for 95% confidence Intervals.	M12

Efficacy: Tables					
No.	Population	GSK Standard/Example Shell	Title	Programming Notes	Deliverable
2.4.	Safety	SNAPSHOT4	Proportion of Subjects with Plasma HIV-1 RNA < 50 c/mL Over Time (Intervention Phase) – Modified Snapshot Analysis with COVID-19 related LOCF	Missing HIV-1 RNA due to COVID-19 are imputing using last post baseline value carried forward. Use Exact (Clopper-Pearson) method for 95% confidence Intervals.	M12
2.5.	Safety	SNAPSHOT7	Summary of Study Outcomes (50 c/mL cutoff) at Month 12 by Site Type (Intervention Phase) – Modified Snapshot Analysis with COVID-19 related LOCF	Missing HIV-1 RNA due to COVID-19 are imputing using last post baseline value carried forward.	M12
CVF					
2.6.	Safety	VF1	Cumulative Proportion of Subjects Meeting Confirmed Virologic Failure Criteria Over Time (Intervention Phase)		HL, M12
2.7.	Safety	207966/primary_15/T2.23	Cumulative Proportion of Subjects Meeting Confirmed Virologic Failure Criteria Over Time		M12, EOS
CD4					
2.8.	Safety	LB1	Summary of CD4+ Cell Count (cells/mm ³) by Visit		M12, EOS
2.9.	Safety	LB1	Summary of Change from Baseline in CD4+ Cell Count (cells/mm ³) by Visit		M12, EOS

Efficacy: Tables					
No.	Population	GSK Standard/ Example Shell	Title	Programming Notes	Deliverable
HIV Associated Conditions					
2.10.	Safety	CDC2	Summary of Post-Baseline CDC Stage 3 HIV-1 Associated Conditions Including Recurrences		M12, EOS
2.11.	Safety	CDC2	Summary of Post-Baseline CDC Stage 3 HIV-1 Associated Conditions Excluding Recurrences		M12, EOS
Plasma HIV-1 RNA					
2.12.	Safety	209493/primary_01/T2.4	Proportion of Subjects with Plasma HIV-1 RNA < 50 c/mL Over Time – Observed Case		EOS

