7.1.3. Strategy for Intercurrent (Post-Randomization) Events

- Participants with last available HIV-1 RNA measurement less than 50 copies/mL while the participant is on treatment within the analysis visit window of interest are classified as HIV-1 RNA < 50 c/mL. Participants without evaluable HIV-RNA data for the visit of interest or who change treatment not permitted per protocol before the analysis window are considered non-responders.
- Participants with last available HIV-1 RNA measurement greater or equal to 50 copies/mL while the participant is on treatment within the analysis visit window of interest are classified as HIV-1 RNA ≥ 50 c/mL. Participants without evaluable HIV-RNA data for the visit of interest and who discontinue treatment for reasons not related to adverse event while having HIV-1 RNA ≥ 50 copies/mL at time of

discontinuation or who change study treatment not permitted per protocol before the analysis window are also classified as having HIV-RNA ≥ 50 copies/mL.

Missing viral load values for reasons related to COVID-19 issues (e.g. participant is unable to have viral load assessed due to barriers in attending the clinic during the pandemic or COVID-19 related adverse events leading to treatment discontinuation) will be imputed using an LOCF approach in which the last on-treatment viral load value will be carried forward and used in place of missing values.

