13.4. Appendix 4: Study Phases and Treatment Emergent Adverse Events

13.4.1. Study Phases

AEs will be assigned to study phases as defined in Table 6. Laboratory data (efficacy, safety, and virology), HIV associated Conditions, health outcomes assessments, vital signs, and ECGs will be assigned to study phases as defined in Table 7.

Assessments/events are assigned to study phases sequentially, starting from the top of each table.

Table 6 Study Phases for AEs

Study Phase	Definition
Screen	Date < Intervention Phase Treatment Start Date
Intervention	
For subjects continuing into the Extension Phase: Intervention Phase Treatment Start Date \leq Date < Date of Nominal Month 13 Visit
 
For subjects not continuing into the Extension Phase: Intervention Phase Treatment Start Date \leq Date < LTFU ART Start Date [a]
 
For AEs leading to treatment withdrawal with start date equal to the LTFU ART Start Date, Intervention Phase instead of Long-term Follow-up Phase will be assigned.

Extension Phase	
Date of Nominal Month 13 Visit \leq Date < LTFU ART Start Date [a]
 
For AEs leading to treatment withdrawal with start date equal to the LTFU ART Start Date, Extension Phase instead of Long-Term Follow-up Phase will be assigned.

Long Term Follow-Up	
For subjects who receive at least one CAB/RPV injection and permanently discontinue study treatment: AE Start Date \geq LTFU ART Start Date
 
AEs with completely missing start date:
 
 • If AE end date is \leq Intervention Phase Treatment Start Date, then assign to Screening Phase; • Else if AE end date is completely missing or Intervention Phase Treatment Start Date $<$ AE end date \leq Date of Nominal Month 13 Visit, then assign to Intervention Phase; • Else if AE end date $>$ Date of Nominal Month 13 Visit, then assign to Extension Phase.

Date=AE Start Date

- [a] If participants have missing LFTU ART start date, only the lower bound will be considered in the derivation.

Table 7 Study Phases for Laboratory, PK, ECG, Vital Signs, HIV-1 Associated Conditions, and Protocol Deviation Data

Study Phase	Definition
Screen	Date ≤ Study Treatment Start Date
Intervention	
For subjects continuing into the Extension Phase: Intervention Phase Treatment Start Date < Date < Date of Nominal Month 13 Visit
 
For subjects not continuing into the Extension Phase: Intervention Phase Treatment Start Date < Date ≤ LTFU ART Start Date ^[a]

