13.4.2. Treatment State

Within each study phase (based on assignment of study phase described in Section 13.4.1), only those events/assessments which occur within the ranges shown in Table 10 will be considered ‘on-treatment’ for the given phase. No treatment states will be assigned to medications.

For adverse events, partial AE start date will use imputation as described in 13.7.2.1.

Table 10 Treatment State within Study Phases

Study Phase	State	Definition
Screen	Pre-Treatment	All assessments/events within phase
Intervention/Extension	On-treatment	Date \leq max (Date of Last CAB LA +RPV LA IM Dose + 35, Date of Last Dose of Oral Study Treatment (CAB+RPV or SOC Bridging) +1)
	Post-Treatment	Date $>$ max (Date of Last CAB LA +RPV LA IM Dose + 35, Date of Last Dose of Oral Study Treatment (CAB+RPV or SOC Bridging) +1)
Long Term Follow-Up	Post-Treatment	All assessments/events within phase

NOTES:

- Date = Assessment/Start Date
- a. Treatment State is determined after data has been assigned to the study phases as defined in Section 13.4.1.
- b. Last injection and/or last dose of oral study treatment (CAB+RPV or SOC bridging) are only applied to participants who permanently discontinued the study treatment. The assessments for participants who did not permanently discontinue the study treatment will be considered 'On-treatment'. For participants continuing into extension phase, all data assigned to intervention phase per Section 13.4.1 will be considered 'On-treatment'

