13.7.2.2. Handling of Missing Data for Statistical Analysis

Element	Reporting Detail
Snapshot	
• In the Snapshot dataset, subjects without HIV – 1 RNA data in the assessment window for the visit of interest (due to missing data or discontinuation of IP prior to the visit window) do not belong to 'HIV-1< 50 c/mL (or 200 c/mL) The nature of this missing data will be further classified in Snapshot summaries as either 'HIV-1 RNA≥50' or 'No Virologic Data at Week X';• See Appendix 9: Snapshot Algorithm Details
LOCF (COVID-19 Related)	
• Missing HIV-1 RNA values within an analysis visit for reasons related to COVID-19 will be imputed using the last on-treatment value from earlier analysis timepoints.• This approach will be used in the primary snapshot analysis to address missing data due to COVID-19.

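### The COVID-19 LOCF rule carries the last on-treatment viral load in the SAP text but the last post-baseline viral load in six display notes

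*SAP*

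**What the plan says.** All references are to the current SAP (RAP Amendment 1).

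- **Section 7.1.3**, on intercurrent events: for viral loads missing for COVID-19 reasons, "the last on-treatment viral load value will be carried forward and used in place of missing values". One of its two examples of such a reason is "COVID-19 related adverse events leading to treatment discontinuation".
- **Section 13.7.2.2**, on missing data: the missing value "will be imputed using the last on-treatment value from earlier analysis timepoints". The section assigns this approach to the primary Snapshot analysis.
- **Section 13.13.5**, programming notes for Tables 2.1, 2.3, 2.4 and 2.5: "Missing HIV-1 RNA due to COVID-19 are imputing using last post baseline value carried forward". Section 13.13.6 repeats the note for Figures 2.1 and 2.2.

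The notes drop two limits: that the value be on treatment, and that it come from an earlier analysis timepoint. The October 2020 RAP, reproduced in the same file, has the same two wordings, so the amendment did not create the conflict.

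**The concern.** LOCF is defined by which value is eligible to be carried. Here the plan gives two eligibility rules for one imputation and no order of precedence. Section 7.1.4 sends the reader to Appendix 13 for display details, which is where the looser wording sits. Two programmers could each follow the plan and classify the same participant differently.

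The looser rule would also be the wrong one for this endpoint. A viral load taken after study treatment has lapsed does not describe the outcome on study treatment, and the Snapshot algorithm in Appendix 9 does not otherwise accept such values. Table 2.1 is among the Month 12 headline deliverables, so a misclassification would appear in a prominent display.

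**Working it through.** The plan gives no figure to reproduce. The check is whether the two wordings can differ under the plan's own definitions, for whom, and by how much.

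**1. Are the terms equivalent?** Table 10 treats all screening-phase data as pre-treatment, so every on-treatment value is post-baseline. The reverse does not hold. Table 10 defines a post-treatment state inside the Intervention/Extension phase, which begins after

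max(last injection + 35 days, last oral study dose + 1 day).

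Table 7 keeps laboratory data in the Intervention Phase for participants not entering the Extension while "Intervention Phase Treatment Start Date < Date ≤ LTFU ART Start Date". A viral load between those two limits is post-baseline and in the Intervention Phase, but off treatment.

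**2. For whom do the rules differ?** Note b to Table 10 says: "Last injection and/or last dose of oral study treatment (CAB+RPV or SOC bridging) are only applied to participants who permanently discontinued the study treatment". Everyone else's post-baseline values count as on-treatment, so the rules agree for them. They can differ only if the participant

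- permanently discontinued study treatment,
- has HIV-1 RNA missing for a COVID-19 reason (Section 7.1.3 expressly includes discontinuers), and
- has a later off-treatment value before LTFU ART start. If that start date is missing, footnote a to Table 7 removes the upper bound, and any later value qualifies.

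The outcome changes only if that later value and the last on-treatment value lie on opposite sides of 50 c/mL.

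**3. Illustration (all dates and values assumed).** Last oral dose Day 30; last injection Day 200; COVID-19-related discontinuation; LTFU ART start Day 270; viral load 39 c/mL on Day 180 and 400 c/mL on Day 250.

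- End of on-treatment state: max(200 + 35, 30 + 1) = Day 235.

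| Rule | Value carried | Month 12 outcome |
|---|---|---|
| Last on-treatment (7.1.3, 13.7.2.2) | 39 c/mL, Day 180 | below 50 c/mL |
| Last post-baseline, Intervention Phase (display notes) | 400 c/mL, Day 250 | 50 c/mL or above |

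Table 2 would slot the Day 250 value to Follow-up rather than to a Month window. The note, read literally, uses it anyway.

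**4. Size.** With the planned N = 115 (Section 2.3), one participant is 1/115 = 0.87 percentage points. The SAP does not say how many would be affected. For an assumed 0 to 2 participants at or above 50 c/mL, the Clopper-Pearson 95% intervals are:

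| Count | Proportion | 95% CI |
|---|---|---|
| 0/115 | 0% | 0 to 3.16% |
| 1/115 | 0.87% | 0.02 to 4.75% |
| 2/115 | 1.74% | 0.21 to 6.14% |

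Table 2.5 splits results by five site types. If these were equal in size (an assumption), each would hold 115/5 = 23 participants, and one reclassification would move a site-type result by 1/23 = 4.3 points.

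**The case against.** The strongest reply is that the governing rule is clear and the note is shorthand for it. Sections 7.1.3 and 13.7.2.2 agree with each other, Section 13.6.3 classifies on values taken while on treatment in the Intervention Phase, and the viral-load conditions in Appendix 9 are framed on treatment. A programmer would have to set all of that aside, and carry a Follow-up record into Month 12, to go wrong. This makes an error unlikely. It does not settle the conflict, because no precedence rule is stated and the note is the instruction attached to the display.

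Two stronger readings are tempting, and the document does not support them.

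- *Suppression on a replacement regimen could be counted as a study-treatment result.* This route is largely closed. All six displays are titled as Intervention Phase, and for injected participants who discontinue, Table 7 places values after LTFU ART start in Long Term Follow-Up. It opens mainly when the LTFU ART start date is missing.
- *An off-treatment value could decide the trial's main result.* Section 7 makes virologic efficacy a secondary objective and bases the primary analysis on implementation measures. Section 2.4 plans no hypothesis test. Table 2.2, also a headline deliverable, has no LOCF, and Listing 10 shows both original and imputed outcomes. A difference would therefore be visible, although neither display says which rule should have been used.

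**Conclusion.** The inconsistency is real and is in the current SAP. The display notes as written admit values that Sections 7.1.3 and 13.7.2.2 exclude, and following them literally could give a wrong imputed outcome. The direct route is a rebound measured after the on-treatment period ends and before LTFU ART begins.

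The likely effect is small: 0.87 percentage points per reclassified participant at N = 115, on a secondary descriptive endpoint, in a group that may be empty. That size rests on the planned N; the number affected cannot be derived from the document. The point merits correction because the rule is wrong as written and easily put right, not because a material shift in the Month 12 result is expected.

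**What to change.** In the notes for Tables 2.1, 2.3, 2.4 and 2.5 and Figures 2.1 and 2.2, replace the reference to the last post-baseline value with: *last on-treatment (Table 10) post-baseline value from an earlier analysis timepoint; no imputation if no such value exists*. This matches Sections 7.1.3 and 13.7.2.2. The final clause is largely covered already, since Appendix 9 has no-virologic-data categories for participants without an on-treatment viral load, but stating it removes doubt.

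The cost is wording in six display notes, with no change to data collection. If the displays have already been programmed, check which rule the code applies and, using Listing 10, whether any participant's outcome differs.
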